Study Measures. The domains chosen for study measures are based on the Integrated Model of Behavior^{45,46} and Ottawa Decision Framework⁴⁷ as well as results of our R21 study of decision-making and CPM.

Background Information. Participant will complete demographic information (i.e., age, race, ethnicity, marital status, education, and occupation). Medical variables (i.e., date of breast cancer diagnosis, method of detection, tumor histology, nuclear grade, stage, human epidermal growth factor receptor (HER2/neu), estrogen receptor (ER) and progesterone receptor (PR) status, and weight and height at diagnosis) will be extracted from patients' charts.

Cancer-Specific Distress. Cancer-specific distress will be measured with the Revised Impact of Events Scale (IES). The IES assesses two common categories of responses to stressful events: intrusion and avoidance. The IES has good internal consistency reliability (0.70 to 0.85).⁴⁸ For this study, patients will be asked to rate the frequency of intrusive thoughts and avoidance behaviors related to their cancer.^{48,49}

Breast Cancer Worry Scale. Breast cancer worry will be assessed with a 4-item scale developed by Lerman et al.^{49,50} These items assess the extent to which worry about breast cancer interferes with women's daily functioning.

Fear of Cancer Recurrence. Fear of recurrence will be assessed with a 5-item scale that measures patients' beliefs and anxieties about disease recurrence.^{51,52} It has been used with a variety of cancer populations and the psychometric properties of this measure have been well-established.^{53,54}

Satisfaction with Decision Scale. A measure of women's satisfaction with their surgery decision.⁵⁵ It has been used with a variety of healthcare decisions

and has been shown to have good reliability and validity.⁵⁵ It will be administered at 1, 6, 12 and 18 months post-surgery.

Decisional Regret. This brief scale measures distress or remorse about the surgical decision.⁵⁶ It has been used to assess regret with a variety of healthcare decisions and has been shown to be reliable and valid.⁵⁶ It will be administered at 1,6,12 and 18 month assessments.

4.0 Statistical Considerations.

Analytic Methods:

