Missing Data. Because we are using patient-reported outcomes, some individuals will fail to complete all questionnaires. PROC GLM in SAS is designed to handle this type of missing data and will give unbiased estimates of effects over time provided that the probability of having missing data depends only on the covariates in the model. We will check this assumption by looking at predictors of missing data. We will also run analyses to examine whether study participants who drop out of the study early differ from those who do not. With the use of PROC GLM, we will be able to include all participants in the analysis, even those with missing values for some time points and those who drop out early. We will also use alternative multiple imputation methods to estimate missing values using differing assumptions if the data appear to not be missing at random. Several

strategies will be used to decrease the chance of missing data and non-compliance. Forms will be reviewed upon receipt to ensure all items are completed, and if incomplete, participants will be contacted to determine if the question was deliberately skipped and, if not, to get a response. Patients will be contacted numerous times by mail and by phone to ensure questionnaire completion. Scheduling of follow-up visits will coincide with clinic visits, and as such, missing data will be kept at a minimum.

Sample size: Given information from the recently completed R21 study and rates over the past 5 years, we estimate that approximately 11.5% of women meeting eligibility criteria will have CPM. All power analyses assume a significance level of 0.05 and a two-sided test. Assuming a 10% attrition rate and an additional loss of 10% of patients due to eligibility changes post-enrollment, we will enroll approximately 345 participants to ensure that approximately 311 participants continue on study to yield complete data on at least 280 participants. Therefore, about 32 women will have CPM, and 248 will not. For comparisons of these two groups of women, a sample size of 280 (32 in the CPM group and 248 in the non CPM group) at 18 months post-surgery will provide 80% power to detect an effect size of 0.54 or greater for the continuous dependent variables.

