Since the primary psychosocial outcomes (such as decisional regret distress and scale) include repeated measurements that are correlated within subjects, our approach will utilize linear mixed model analysis (LMM, a special case of generalized linear mixed modeling in which each outcome variable is continuous). For the LMM analyses of continuous dependent variables across time (baseline, 1, 6, 12, and 18 months post-surgery), we calculated detectable effects based on a wide range of homogeneous correlations, namely, 0.3, 0.5, and 0.7, between repeated measurements. To simplify the power calculation procedure, we assume that there is no interaction between treatment and time points. The detectable effects of treatment are presented in Table 3. The calculations were done using PASS 2005 (Power Analysis and Sample Size Software). We provide a brief explanation of the results presented in the first row. In the first row, the homogeneous correlation between treatments across time points is assumed to be 0.3. A sample size of 259 (32 in the CPM group and 227 in the non CPM group) will provide 80% power to detect a standard deviation (SD) in means across groups of 0.10 (an effect size of 0.19), which corresponds to the means of 0, 0.290 (in SD unit) in the two groups. The above figure provides the power plot by effect size on treatment when the correlations (r) are 0.3, 0.5, and 0.7, respectively.

[figure not shown]

Table 3. Detectable treatment effects over time using LMM analysis with 80% power

Correlation between assessment (r)	Detectable mean diffs effects on treatment	SD of effect on treatment	Effect Size among treatment
0.3	0, 0.290	0.10	0.19
0.5	0, 0.306	0.11	0.19
0.7	0, 0.340	0.12	0.19

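### Table 3 claims 80% power for differences of 0.290, 0.306 and 0.340 SD, but the stated inputs give about 53% to 64%

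*Combined protocol and SAP*

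**What the plan says.** Section 4.0 (Sample size) makes two power statements, both governed by one sentence: "All power analyses assume a significance level of 0.05 and a two-sided test".

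- **Single time point.** The plan takes "a sample size of 280 (32 in the CPM group and 248 in the non CPM group) at 18 months post-surgery" and gives 80% power for an effect size of 0.54.
- **Repeated measures.** "For the LMM analyses of continuous dependent variables across time (baseline, 1, 6, 12, and 18 months post-surgery", the plan uses a "wide range of homogeneous correlations, namely, 0.3, 0.5, and 0.7, between repeated measurements" and assumes no group-by-time interaction. The first row is explained in words: "A sample size of 259 (32 in the CPM group and 227 in the non CPM group" and this "will provide 80% power to detect a standard deviation (SD) in means across groups of 0.10 (an effect size of 0.19", corresponding to means of 0 and 0.290 SD.

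Table 3, titled "Detectable treatment effects over time using LMM analysis with 80% power", lists:

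| r | Difference (SD) | SD of means | Effect size |
|---|---|---|---|
| 0.3 | 0.290 | 0.10 | 0.19 |
| 0.5 | 0.306 | 0.11 | 0.19 |
| 0.7 | 0.340 | 0.12 | 0.19 |

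The primary outcome named in section 1.0 is decisional regret. Section 3.0 (Study Measures) says of that scale: "It will be administered at 1,6,12 and 18 month assessments". That is four assessments with no baseline.

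**The concern.** Averaging equally correlated measurements reduces variance only down to the correlation itself, so the gain over a single assessment shrinks quickly as r rises. Going from 0.54 SD at one visit to 0.340 SD at r = 0.7 is a larger gain than that structure allows. The tabulated differences also rise too slowly from row to row for a table that holds the effect size at 0.19 throughout.

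Table 3 is the only power statement for the mixed-model analysis. If it is too optimistic, a null result on regret could be read as having had 80% power near 0.3 SD when the real figure was little better than even. The study is meant to inform women about an irreversible choice, so misplaced reassurance from a null result matters.

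**Working it through.** **Inputs (section 4.0).** Two-sided alpha 0.05; n1 = 32, n2 = 227; m = 5 assessments; equal correlation r; no interaction, so the test is the group main effect. The SD unit is taken as the SD of a single assessment.

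**The plan's single-visit figure.** With 32 and 248, power at 0.54 SD is 81.7% (noncentral t), so that statement holds.

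**Formulas for the repeated-measures case.**
- Variance of a woman's mean score: v = (1 + (m − 1)r)/m
- SE = sqrt(v × (1/32 + 1/227)) = 0.1888 × sqrt(v)
- Difference with 80% power, 257 df: 2.812 × SE

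**Five assessments**

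| r | v | SE | Table 3 | Power at Table 3 value | 80%-power difference | Ratio to Table 3 |
|---|---|---|---|---|---|---|
| 0.3 | 0.44 | 0.1253 | 0.290 | 63.6% | 0.352 | 1.21 |
| 0.5 | 0.60 | 0.1463 | 0.306 | 54.9% | 0.411 | 1.34 |
| 0.7 | 0.76 | 0.1646 | 0.340 | 53.9% | 0.463 | 1.36 |

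A simulation of subject means (20,000 runs per row) gave 63.1%, 54.5% and 54.3%.

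**Four assessments (decisional regret)**

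| r | v | SE | Power at Table 3 value | 80%-power difference |
|---|---|---|---|---|
| 0.3 | 0.475 | 0.1301 | 60.3% | 0.366 |
| 0.5 | 0.625 | 0.1493 | 53.3% | 0.420 |
| 0.7 | 0.775 | 0.1662 | 53.1% | 0.467 |

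**Floor.** As m grows without limit, v tends to r and the 80%-power difference tends to 0.291, 0.375 and 0.444 SD. Rows 2 and 3 of Table 3 lie well below this floor. Row 1 sits at it.

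**Cross-check from the plan's own 0.54.** Multiplying by sqrt(v) for five visits gives 0.54 × 0.663 = 0.358, 0.54 × 0.775 = 0.418 and 0.54 × 0.872 = 0.471.

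**Shape of the table.** With a constant effect size, the differences should rise as sqrt(v), in the ratio 1 : 1.17 : 1.31. Table 3 rises 1 : 1.06 : 1.17. A different N rescales all rows alike, so it cannot repair this.

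**Other columns.** With p = 32/259, the SD of two group means is d × sqrt(p(1 − p)) = 0.329d. This gives 0.095, 0.101 and 0.112, against 0.10, 0.11 and 0.12 in the table; row 1 agrees after rounding. Dividing by sqrt(v) gives effect sizes f of 0.144, 0.130 and 0.128, not 0.19. A two-group test at N = 259 needs f = 0.175 for 80% power.

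**Alternative readings tried**

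| Variant (five visits unless stated) | Power at 0.290 / 0.306 / 0.340 |
|---|---|
| 32 and 248 | 64.0% / 55.4% / 54.3% |
| All 345 enrolled (about 40 and 305) | 73.6% / 64.9% / 63.8% |
| One-sided test | 74.7% / 67.1% / 66.1% |
| First-order autoregressive correlation | 76.9% / 67.7% / 62.8% |
| Baseline-adjusted, four follow-ups | 69.4% / 75.1% / 91.9% |

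None reproduces the table. Under baseline adjustment the detectable difference falls as r rises, the opposite of Table 3, and regret has no baseline to adjust for.

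**N needed.** Reaching 80% power at the tabulated differences with the same group ratio takes about 381, 466 and 479 women with five visits, or 411, 486 and 488 with four.

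**The two totals.** The plan gives 280 (32 and 248) and 259 (32 and 227). 32/280 is 11.4%, which fits the assumed 11.5% CPM rate; 32/259 is 12.4%.

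**The case against.** The strongest reply is that the enrolment of 345 is presented with the 18-month comparison, which is correctly powered, and that the corrected repeated-measures differences are still smaller than 0.54 SD. No sample size, outcome, test or visit has to change, and final results will be read from estimates and confidence intervals. This stands as a limit on the consequences. It does not make the table right: the plan states a power that the design does not deliver, in the optimistic direction in every row.

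It is also fair to say that only decisional regret and satisfaction with the decision are limited to four assessments; the other scales are not restricted in this way. The 54% to 64% range therefore answers Table 3 as written, and 53% to 60% applies to regret. The choice moves the detectable differences by at most 0.014 SD.

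The effect-size column, taken alone, errs the other way: f = 0.19 with two groups and N = 259 would have 86% power. It shows that the columns disagree, and adds nothing to the claim of optimism. A three-group test at N = 259 would need f = 0.194, which may be where 0.19 came from, but the software output and the power plot are not available, so the cause cannot be established. The SD-column errors and the 259/280 mismatch are minor; the mismatch changes power by less than one percentage point.

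**Conclusion.** The concern holds. Under the plan's own assumptions, power at the Table 3 differences is 64%, 55% and 54% with five assessments, and 60%, 53% and 53% with the four that apply to the primary outcome. The correct 80%-power differences are 21% to 37% larger than stated. The result rests on equal correlations, no interaction, complete data on the stated numbers, and reading the SD unit as the SD of one assessment. Reading it as a residual SD would lower power further. The 18-month statement is sound, so the error is confined to the repeated-measures paragraph and Table 3.

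**What to change.** Recalculate Table 3 with a single N of 280 (32 and 248) and the four post-surgery assessments of decisional regret:

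| r | Detectable difference (SD) | SD of means | Effect size f |
|---|---|---|---|
| 0.3 | 0.364 | 0.116 | 0.168 |
| 0.5 | 0.417 | 0.133 | 0.168 |
| 0.7 | 0.465 | 0.148 | 0.168 |

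Here the SD of means is the difference × sqrt(p(1 − p)) with p = 32/280, and f is that SD divided by sqrt(v).

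Label the table as applying to outcomes measured four times. If scales with a baseline are also to be covered, add the five-assessment values for 32 and 248: 0.350, 0.409 and 0.460 SD. Rewrite the first-row explanation and redraw the power plot to match, and replace 259 (32 and 227) with 280 (32 and 248) throughout.

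Enrolment stays at 345. The cost is a text, table and figure correction, and a less favourable stated sensitivity.
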